5.1.2 Participant Exclusion Criteria					

Participants are excluded from the study if any of the following criteria apply:

- 1. A WOCBP who has a positive serum pregnancy test within 24 hours prior to the first dose of study intervention (see Appendix 3).
- Has received prior therapy with an anti-PD-1, anti-PD-L1, or anti-PD-L2 agent or with an agent directed to another stimulatory or co-inhibitory T-cell receptor (e.g., CTLA-4, OX-40, CD137). Prior therapy with Tebentafusp is permitted. Prior liver directed therapy is permitted (including but not limited to radioembolization, chemoembolization, immunoembolization, radiofrequency ablation, external beam radiation and resection).
- 3. Participants previously treated with radiation therapy must have recovered from all radiationrelated toxicities and not require corticosteroids.
- 4. Has received a live vaccine or live-attenuated vaccine within 30 days prior to the first dose of study drug. Administration of killed-virus vaccines and mRNA vaccines are allowed.
- 5. Has a diagnosis of immunodeficiency or is receiving chronic systemic steroid therapy (in dosing exceeding 10 mg daily of prednisone equivalent) or any other form of immunosuppressive therapy within 7 days prior to the first dose of study drug.
- 6. Has a known additional malignancy that is progressing or has required active treatment within the past 3 years. Participants with basal cell carcinoma of the skin, squamous cell carcinoma of the skin, early stage bladder cancer, or carcinoma in situ (e.g., breast carcinoma, cervical cancer in situ) that have undergone potentially curative therapy are not excluded.
- 7. Has known active CNS metastases and/or carcinomatous meningitis. Participants with previously treated brain metastases may participate provided they are radiologically stable, i.e.

Confidential

without evidence of progression for at least 4 weeks by repeat imaging (note that the repeat imaging should be performed during study screening), clinically stable and without requirement of steroid treatment for at least 14 days prior to first dose of study intervention.

- 8. Has severe hypersensitivity (≥Grade 3) to pembrolizumab and/or any of its excipients.
- 9. Has active autoimmune disease that has required systemic treatment in the past 2 years (i.e. with use of disease modifying agents, corticosteroids or immunosuppressive drugs). Replacement therapy (e.g., thyroxine, insulin, or physiologic corticosteroid replacement therapy for adrenal or pituitary insufficiency, etc.) is not considered a form of systemic treatment and is allowed.
- 10. Has a history of (non-infectious) pneumonitis/interstitial lung disease that required steroids or has current pneumonitis/interstitial lung disease.
- 11. Has an active infection requiring systemic therapy.
- 12. Has a history or current evidence of any condition, therapy, or laboratory abnormality that might confound the results of the study, interfere with the participant's participation for the full duration of the study, or is not in the best interest of the participant to participate, in the opinion of the treating investigator.
- 13. Has known psychiatric or substance abuse disorders that would interfere with cooperation with the requirements of the trial.
- 14. Is pregnant or breastfeeding or expecting to conceive or father children within the projected duration of the study, starting with the screening visit through 120 days after the last dose of trial treatment.
- 15. Has had an allogenic tissue/solid organ transplant.
- 16. Uncontrolled blood pressure (Systolic BP>140 mmHg or diastolic BP >90 mmHg) in spite of an optimized regimen of antihypertensive medication.
- 17. Significant cardiovascular impairment: history of congestive heart failure greater than New York Heart Association (NYHA) Class II, unstable angina, myocardial infarction or stroke within 6 months of the first dose of study drug, or cardiac arrhythmia requiring medical treatment at Screening.
- 18. Bleeding or thrombotic disorders or subjects at risk for severe hemorrhage. The degree of tumor invasion/infiltration of major blood vessels (e.g. carotid artery) should be considered because of the potential risk of severe hemorrhage associated with tumor shrinkage/necrosis following lenvatinib therapy.

- 19. Subjects having $\geq 2+$ proteinuria on urine dipstick testing. However, subjects with $\geq 2+$ proteinuria on urine dipstick testing may undergo a 24-hour urine collection for quantitative assessment of proteinuria. Subjects with <1 g/24-hour proteinuria are eligible for participation.
- 20. Subjects who have not recovered adequately from any toxicity from other anti- cancer treatment regimens and/or complications from major surgery prior to starting therapy. Withhold lenvatinib for at least 1 week prior to elective surgery. Do not administer for at least 2 weeks following major surgery and until adequate wound healing.
- 21. Females who are breastfeeding or pregnant at Screening or Baseline (as documented by a positive beta-human chorionic gonadotropin [β-hCG] (or human chorionic gonadotropin [hCG]) test with a minimum sensitivity of 25 IU/L or equivalent units of β-hCG [or hCG]).
- 22. Females of child-bearing potential must be willing to use effective contraception during study and for 120 days after the last dose
- 23. The participant has severe hypersensitivity (≥Grade 3) to lenvatinib and/or any of its excipients

5.1.3 Lifestyle Considerations

5.1.3.1 Meals and Dietary Restrictions

Participants should maintain a normal diet unless modifications are required to manage an AE such as diarrhea, nausea or vomiting.

5.1.3.2 Contraception

Pembrolizumab and lenvatinib may have adverse effects on a fetus in utero. Refer to Appendix 3 for approved methods of contraception.

For this study, male participants will be considered to be of non-reproductive potential if they have azoospermia (whether due to having had a vasectomy or due to an underlying medical condition).

5.1.3.3 Pregnancy

If a participant inadvertently becomes pregnant while on treatment with pembrolizumab and lenvatinib, the participant will be immediately discontinued from study intervention(s). The site will contact the participant at least monthly and document the participant's status until the pregnancy has been completed or terminated. The outcome of the pregnancy will be reported to Merck within 2 working days if the outcome is a serious adverse experience (e.g. death, abortion, congenital anomaly, or other disabling or life-threatening complication to the mother or newborn). The study Investigator will make every effort to obtain permission to follow the outcome of the pregnancy and report the condition of the fetus or newborn to Merck. If a male participant impregnates his female partner, the

study personnel at the site must be informed immediately and the pregnancy must be reported to Merck and followed as described in Section 6.2.

5.2 Trial Intervention(s)

The intervention(s) to be used in this trial is outlined below in Table 3.

Table 3 Trial Intervention(s)

Drug	Dose/Potency	Dose Frequency	Route of Administration	Regimen/Treatment Period	Use		
Lenvatinib	20 mg	QD	Oral	QD, no treatment duration limit	Experimental		
Pembrolizumab	200 mg	Q3W	IV infusion	Day 1 of each 3-week cycle for 2 years maximum	Experimental		
Abbreviations: IV = intravenous; QD = once daily							

Trial intervention(s) should begin on the day of or as close as possible to the date on which intervention is allocated/assigned.

5.2.1 Timing of Dose Administration

Trial interventions should be administered on Day 1 of each cycle after all procedures/assessments have been completed as detailed on the Schedule of Activities, Section 2.3. Trial interventions may be administered up to 3 days before or after the scheduled Day 1 of each cycle due to administrative reasons.

All trial interventions will be administered on an outpatient basis.

Pembrolizumab 200 mg will be administered as a 30 minute IV infusion every 3 weeks. Sites should make every effort to target infusion timing to be as close to 30 minutes as possible. However, given the variability of infusion pumps from site to site, a window of -5 minutes and +10 minutes is permitted (i.e., infusion time is 30 minutes: $-5 \min/+10 \min$).

The Pharmacy Manual contains specific instructions for the preparation of the pembrolizumab infusion fluid and administration of infusion solution.

Lenvatinib 20 mg will be administered in an oral dose to be taken once daily. Capsules are packaged in cold form blisters or high-density polyethylene bottles with a polypropylene cap and desiccant. The blisters and bottles should be stored under room temperature.

AEs associated with pembrolizumab exposure, including coadministration with additional compounds, may represent an immunologic etiology. These immune-related AEs (irAEs) may occur shortly after the first dose or several months after the last dose of pembrolizumab/combination treatment and may affect more than one body system simultaneously. Therefore, early recognition and initiation of treatment is critical to reduce complications. Based on existing clinical study data, most irAEs were reversible and could be managed with interruptions of pembrolizumab/combination treatment, administration of corticosteroids and/or other supportive care. For suspected irAEs, ensure adequate evaluation to confirm etiology or exclude other causes. Additional procedures or tests such as bronchoscopy, endoscopy, skin biopsy may be included as part of the evaluation. Dose modification and toxicity management guidelines for irAEs associated with pembrolizumab/combination treatment are provided in Table 4.

Attribution of Toxicity:

When study interventions are administered in combination, attribution of an adverse event to a single component is likely to be difficult. Therefore, while the investigator may attribute a toxicity event to lenvatinib or to pembrolizumab alone, both interventions must be held according to the criteria in Table 4 Dose Modification and Toxicity Management Guidelines for Immune-Related Adverse Events Associated with Pembrolizumab.

Holding Study Interventions:

When study interventions are administered in combination, if the AE is considered immune-related, both interventions should be held according to recommended dose modifications.

Restarting Study Interventions:

Participants may not have any dose modifications (no change in dose or schedule) of pembrolizumab in this study, as described in Table 4.

- If the toxicity does not resolve or the criteria for resuming treatment are not met, the participant must be discontinued from all study interventions.
- If the toxicities do resolve and conditions are aligned with what is defined in Table 4, the combination of lenvatinib and pembrolizumab may be restarted at the discretion of the investigator. In these cases where the toxicity is attributed to the combination or to lenvatinib alone, re-initiation of pembrolizumab as a monotherapy may be considered at the principal investigator's discretion.

Table 4 Dose modification and toxicity management guidelines for immune-related AEs associated with pembrolizumab monotherapy and Immunotherapy (IO) Combinations

General instructions:

- 1. Severe and life-threatening irAEs should be treated with IV corticosteroids followed by oral steroids. Other immunosuppressive treatment should begin if the irAEs are not controlled by corticosteroids.
- 2. Study intervention must be permanently discontinued if the irAE does not resolve or the corticosteroid dose is not ≤ 10 mg/day within 12 weeks of the last study intervention treatment.
- 3. The corticosteroid taper should begin when the irAE is \leq Grade 1 and continue at least 4 weeks.
- 4. If study intervention has been withheld, study intervention may resume after the irAE decreased to \leq Grade 1 after corticosteroid taper.

irAEs	Toxicity Grade (CTCAE v5.0)	Action With Pembrolizumab	Corticosteroid and/or Other Therapies	Monitoring and Follow-up		
	Grade 2	Withhold	 Administer corticosteroids (initial dose of 1 to 2 mg/kg prednisone or equivalent) followed by taper 	Monitor participants for signs and symptoms of pneumonitis • Evaluate participants with suspected		
Pneumonitis	Recurrent Grade 2, Grade 3 or 4	Permanently discontinue	 Add prophylactic antibiotics for opportunistic infections 	pneumonitis with radiographic imaging and initiate corticosteroid treatment		
Diarrhea/Colitis	Grade 2 or 3	Withhold	 Administer corticosteroids (initial dose of 1 to 2 mg/kg prednisone or equivalent) followed by taper 	 Monitor participants for signs and symptoms of enterocolitis (i.e., diarrhea, abdominal pain, blood or mucus in stool with or without fever) and of bowel perforation (i.e., peritoneal signs and ileus) 		

irAEs	Toxicity Grade (CTCAE v5.0)	Action With Pembrolizumab	Corticosteroid and/or Other Therapies	Monitoring and Follow-up
	Recurrent Grade 3 or Grade 4	Permanently discontinue		 Participants with ≥Grade 2 diarrhea suspecting colitis should consider GI consultation and performing endoscopy to rule out colitis
				 Participants with diarrhea/colitis should be advised to drink liberal quantities of clear fluids. If sufficient oral fluid intake is not feasible, fluid and electrolytes should be substituted via IV infusion
AST or ALT Elevation or	Grade 2 ^ª	Withhold	 Administer corticosteroids (initial dose of 0.5 to 1 mg/kg prednisone or equivalent) followed by taper 	 Monitor with liver function tests (consider weekly or more frequently until liver enzyme value returned to baseline or is stable)
Increased Bilirubin	Grade 3 ^b or 4 ^c	Permanently discontinue	 Administer corticosteroids (initial dose of 1 to 2 mg/kg prednisone or equivalent) followed by taper 	
T1DM or Hyperglycemia	New onset T1DM or Grade 3 or 4 hyperglycemia associated with evidence of b-cell failure	Withhold ^d	 Initiate insulin replacement therapy for participants with T1DM Administer antihyperglycemic in participants with hyperglycemia 	 Monitor participants for hyperglycemia or other signs and symptoms of diabetes
	Grade 2	Withhold	 Administer corticosteroids and initiate hormonal replacements as clinically indicated 	 Monitor for signs and symptoms of hypophysitis (including hypopituitarism and adrenal insufficiency)
Hypophysitis	Grade 3 or 4	Withhold or permanently discontinue ^d		

irAEs	Toxicity Grade (CTCAE v5.0)	Action With Pembrolizumab	Corticosteroid and/or Other Therapies	Monitoring and Follow-up		
	Grade 2	Continue	 Treat with nonselective beta-blockers (e.g., propranolol) or thionamides as appropriate 	 Monitor for signs and symptoms of thyroid disorders 		
Hyperthyroidism	Grade 3 or 4	Withhold or permanently discontinue ^d				
Hypothyroidism	Grade 2, 3 or 4	Continue	 Initiate thyroid replacement hormones (e.g., levothyroxine or liothyronine) per standard of care 	 Monitor for signs and symptoms of thyroid disorders 		
Nephritis: Grade 2		Withhold	 Administer corticosteroids (prednisone 1 to 2 mg/kg or equivalent) followed by 	· Monitor changes of renal function		
according to increased creatinine or acute kidney injury	Grade 3 or 4	Permanently discontinue	taper			
Neurological	Grade 2	Withhold	 Based on severity of AE administer corticosteroids 	 Ensure adequate evaluation to confirm etiology and/or exclude other causes 		
Toxicities	Grade 3 or 4	Permanently discontinue				
	Grade 1	Withhold	 Based on severity of AE administer corticosteroids 	 Ensure adequate evaluation to confirm etiology and/or exclude other causes 		
Myocarditis	Grade 2, 3 or 4	Permanently discontinue				
Exfoliative	Suspected SJS, TEN, or DRESS	Withhold	 Based on severity of AE administer corticosteroids 	 Ensure adequate evaluation to confirm etiology or exclude other causes 		
Conditions	Confirmed SJS, TEN, or DRESS	Permanently discontinue				

irAEs	Toxicity Grade (CTCAE v5.0)	Action With Pembrolizumab	Corticosteroid and/or Other Therapies	Monitoring and Follow-up
	Persistent Grade 2	Withhold	 Based on severity of AE administer corticosteroids 	 Ensure adequate evaluation to confirm etiology or exclude other causes
All Other irAEs	Grade 3	Withhold or discontinue based on the event ^e		
	Recurrent Grade 3 or Grade 4	Permanently discontinue		
AE(a)-advarga ava	nt(a). AIT = alanina a	min atman afamagas AST-	anostata amin atsan afasaa. CTCAE-Camman Tama	in alagri Cuitania fan Adriana Erranta, DRESS-Dura

AE(s)=adverse event(s); ALT= alanine aminotransferase; AST=aspartate aminotransferase; CTCAE=Common Terminology Criteria for Adverse Events; DRESS=Drug Rash with Eosinophilia and Systemic Symptom; GI=gastrointestinal; IO=immuno-oncology; ir=immune related; IV=intravenous; SJS=Stevens-Johnson Syndrome; T1DM=type 1 diabetes mellitus; TEN=Toxic Epidermal Necrolysis; ULN=upper limit of normal.

Note: Non-irAE will be managed as appropriate, following clinical practice recommendations.

- ^a AST/ALT: >3.0 to 5.0 x ULN if baseline normal; >3.0 to 5.0 x baseline, if baseline abnormal; bilirubin:>1.5 to 3.0 x ULN if baseline normal; >1.5 to 3.0 x baseline if baseline abnormal
- ^b AST/ALT: >5.0 to 20.0 x ULN, if baseline normal; >5.0 to 20.0 x baseline, if baseline abnormal; bilirubin:>3.0 to 10.0 x ULN if baseline normal; >3.0 to 10.0 x baseline if baseline abnormal
- c AST/ALT: >20.0 x ULN, if baseline normal; >20.0 x baseline, if baseline abnormal; bilirubin: >10.0 x ULN if baseline normal; >10.0 x baseline if baseline abnormal
- ^d The decision to withhold or permanently discontinue pembrolizumab is at the discretion of the investigator or treating physician. If control achieved or \leq Grade 2, pembrolizumab may be resumed.
- e Events that require discontinuation include, but are not limited to: encephalitis and other clinically important irAEs (e.g., vasculitis and sclerosing cholangitis).

Dose modification and toxicity management of infusion-reactions related to pembrolizumab

Pembrolizumab may cause severe or life-threatening infusion-reactions including severe hypersensitivity or anaphylaxis. Signs and symptoms usually develop during or shortly after drug infusion and generally resolve completely within 24

hours of completion of infusion. Dose modification and toxicity management guidelines on pembrolizumab associated infusion reaction are provided in Table 5.

NCI CTCAE Grade	Treatment	Premedication at Subsequent Dosing
Grade 1	Increase monitoring of vital signs as medically indicated until the	None
Mild reaction; infusion	participant is deemed medically stable in the opinion of the investigator.	
interruption not indicated;		
intervention not indicated		
Grade 2 Requires therapy or influsion	Stop Infusion.	Participant may be premedicated 1.5h (+ 30 minutes) prior to infusion of
interruption but responds	IV fluids	$(\pm 30 \text{ minutes})$ prior to infusion of study intervention with:
promptly to symptomatic	Antihistamines	Diphenhydramine 50 mg po (or
treatment (e.g., antihistamines,	NSAIDs	equivalent dose of antihistamine).
NSAIDs, narcotics, IV fluids);	Acetaminophen	Acetaminophen 500-1000 mg po (or
prophylactic medications	Narcotics	equivalent dose of analgesic).
indicated for ≤ 24 hrs	Increase monitoring of vital signs as medically indicated until the	
	participant is deemed medically stable in the opinion of the investigator.	
	If symptoms resolve within 1 hour of stopping drug infusion, the infusion	
	may be restarted at 50% of the original infusion rate (e.g. from 100 mL/hr	
	to 50 mL/hr). Otherwise dosing will be held until symptoms resolve and	
	the participant should be premedicated for the next scheduled dose.	
	Participants who develop Grade 2 toxicity despite adequate	
	premedication should be permanently discontinued from further	
	study drug intervention	
Grades 3 or 4	Stop Infusion.	No subsequent dosing
Grade 3:	Additional appropriate medical therapy may include but is not limited to:	
Prolonged (i.e., not rapidly	Epinephrine**	
responsive to symptomatic	IV fluids	
medication and/or brief	Antihistamines	
interruption of infusion);	NSAIDs	
recurrence of symptoms	Acetaminophen	
following initial improvement;	Narcotics	
hospitalization indicated for	Oxygen	
other clinical sequelae (e.g.,	Pressors	
	Corticosteroids	

Table 5 Pembrolizumab Infusion Reaction Dose modification and Treatment Guidelines

renal impairment, pulmonary	Increase monitoring of vital signs as medically indicated until the						
infiltrates)	participant is deemed medically stable in the opinion of the investigator.						
Grade 4:	Hospitalization may be indicated.						
Life-threatening; pressor or	**In cases of anaphylaxis, epinephrine should be used immediately.						
ventilatory support indicated	Participant is permanently discontinued from further study drug						
	intervention.						
Appropriate resuscitation equipment should be available at the bedside and a physician readily available during the period of drug administration.							
For further information, please refer	For further information, please refer to the Common Terminology Criteria for Adverse Events v5.0 (CTCAE) at http://ctep.cancer.gov						

Other allowed dose interruption for pembrolizumab

Pembrolizumab may be interrupted for situations other than treatment-related AEs such as medical / surgical events and/or unforeseen circumstances not related to study intervention. However, intervention is to be restarted within 3 weeks of the originally scheduled dose and within 42 days of the previously administered dose, unless otherwise discussed with the Sponsor. The reason for study intervention interruption is to be documented in the patient's study record.

Dose Modifications for Overlapping Toxicities Pembrolizumab-Lenvatinib:

Based on the known toxicity profiles of pembrolizumab and lenvatinib, certain treatment-related AEs are uniquely associated with one drug versus the other. For example, hypertension, arterial thrombotic events, proteinuria, and hemorrhagic events are known risks for lenvatinib treatment, while immune-related AEs are risks for pembrolizumab treatment. However, certain AEs, such as such as diarrhea, hypothyroidism, and liver enzyme elevation, may be initially considered attributable to either study drug. Therefore, evaluation of attribution is important for determining the study drug most likely related to the AE, or an alternative etiology, and subsequently proper clinical management. The following aspects should be considered:

1. Timing of AE onset

Since lenvatinib is dosed daily and continuously due to a relatively short half-life (28 hours), and pembrolizumab is dosed Q3W due to a long half-life, lenvatinib can be interrupted to assess whether an AE improves/resolves with dechallenge (ie, interruption of treatment) based on the following two scenarios:

- If an AE is identified during a treatment cycle (ie, between 2 pembrolizumab doses), only lenvatinib dose interruption is needed.
- If an AE is identified at the beginning of a treatment cycle, lenvatinib can be interrupted and dosing of pembrolizumab should be held.

If the subject recovers from an AE in response to lenvatinib interruption (ie, positive dechallenge), the event is more likely to be related to lenvatinib. Otherwise, after excluding other alternative explanations, an immune-related AE should be considered.

2. Severity of AE

If an AE is suspected to be treatment related and is severe/life threatening at the time of onset or is rapidly worsened, action including interrupting both drugs and initiating treatment with a corticosteroid (with exception of hypothyroidism, TIDM) and other supportive care should be taken promptly.

- 3. Participants receiving the combination therapy (pembrolizumab + lenvatinib) must discontinue study therapy if any of the following occur:
 - ALT or AST >5 X ULN for more than 2 weeks. Pembrolizumab will have already been permanently discontinued per Table 6,[X], but

Confidential
lenvatinib may be administered at a reduced dose by the time this criterion is met and must be permanently discontinued immediately.

 ALT or AST >3 X ULN and (TBL >2 X ULN or INR >1.5). Although Table [X] advises pembrolizumab to be withheld (interrupted), and Table [X] advises lenvatinib to have no dose modification or a reduction, if this criterion is met, both drugs must be permanently discontinued immediately.

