3.2 Secondary Objective(s), Hypothesis(es), and Endpoint(s)

(1) **Objective**: To evaluate the objective response rate resulting from treatment with Lenvatinib + pembrolizumab.

Hypothesis: Treatment with Lenvatinib + pembrolizumab will result in an improved objective response rate as compared with previously reported therapies including pembrolizumab monotherapy, ipilimumab + nivolumab and tebentafusp.

Secondary Endpoint: Objective response rate (complete and partial responses assessed by iRECIST)

(2) **Objective**: To evaluate the effect of treatment with Lenvatinib + pembrolizumab on overall survival.

Hypothesis: Treatment with Lenvatinib + pembrolizumab will result in improved overall survival as compared with previously reported therapies including pembrolizumab monotherapy, ipilimumab + nivolumab and tebentafusp.

Secondary Endpoint: Overall survival, defined as the time from enrollment to death (resulting from any cause).

(3) **Objective**: To evaluate the safety and tolerability of treatment with Lenvatinib + pembrolizumab in patients with metastatic uveal melanoma.

Hypothesis: Treatment with Lenvatinib + pembrolizumab will demonstrate an acceptable toxicity profile in patients with metastatic uveal melanoma.

Secondary Endpoint:

• Adverse events (per CTCAE v5.0)

• Frequency of treatment interruption, dose reduction, and treatment discontinuation due to treatment related adverse events (TRAE).

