5.3.3 Rescue Medications & Supportive Care

Participants should receive appropriate supportive care measures as deemed necessary by the treating investigator. Suggested supportive care measures for the management of AEs with potential immunologic etiology are outlined along with the dose modification guidelines in Section 5.2.2, [Table 4]. Where appropriate, these guidelines include the use of oral or IV treatment with corticosteroids, as well as additional anti-inflammatory agents if symptoms do not improve with administration of corticosteroids. Note that several courses of steroid tapering may be necessary as symptoms may worsen when the steroid dose is decreased. For each disorder, attempts should be made to rule out other causes such as metastatic disease or bacterial or viral infection, which might require additional supportive care. The treatment guidelines are intended to be applied when the Investigator determines the events to be related to pembrolizumab.

It may be necessary to perform conditional procedures such as bronchoscopy, endoscopy, or skin photography as part of evaluation of the event.

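### Section 5.2.2 gives incompatible holding instructions for toxicities that either drug may cause, with no order of precedence and an unstated scope for the steroid sentence

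*Combined protocol and SAP*

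**What the plan says.** The passages run on after Section 5.2.1 in the body; the table of contents numbers them 5.2.2. Four places set out when a drug is held.

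- **Attribution of Toxicity:** "while the investigator may attribute a toxicity event to lenvatinib or to pembrolizumab alone, both interventions must be held according to the criteria". These criteria are those of Table 4, whose title limits it to immune-related adverse events.
- **Holding Study Interventions** (the next paragraph): "if the AE is considered immune-related, both interventions should be held according to recommended dose modifications".
- **Overlapping Toxicities, item 1:** for events such as diarrhoea, hypothyroidism and liver enzyme elevation, attribution is to guide management. "If an AE is identified during a treatment cycle (ie, between 2 pembrolizumab doses), only lenvatinib dose interruption is needed". If the event is found at the start of a cycle, lenvatinib can be interrupted and pembrolizumab should be held.
- **Table 4:** withhold for Grade 2 or 3 diarrhoea/colitis and for Grade 2 AST/ALT or bilirubin elevation; permanently discontinue for Grade 3 or 4 hepatic elevation; continue for Grade 2 to 4 hypothyroidism.

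On steroids, item 2 of the overlapping-toxicity text calls for "action including interrupting both drugs and initiating treatment with a corticosteroid (with exception of hypothyroidism, TIDM") when an event is suspected to be treatment-related and is severe or life-threatening when it starts, or worsens rapidly. Table 4 refers its steroid instructions to immune-related events, and a note beneath it leaves other events to clinical practice. Section 5.3.3 adds: "The treatment guidelines are intended to be applied when the Investigator determines the events to be related to pembrolizumab".

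Section 3.2 lists as a secondary safety endpoint "Frequency of treatment interruption, dose reduction, and treatment discontinuation due to treatment related adverse events (TRAE"). It does not say whether this is counted per drug or for the regimen.

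**The concern.** Two members of staff who both follow the protocol can reach different holding decisions for the same patient. One holds both drugs by the Table 4 criteria. The other interrupts lenvatinib alone and watches for recovery. The protocol does not say which text governs. For a severe event that is not thought to be immune-related, staff also cannot tell whether the corticosteroid sentence applies.

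The first thing at stake is consistent patient management. The second is the secondary endpoint on interruption, reduction and discontinuation, which would partly reflect which paragraph was followed rather than how the regimen was tolerated.

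**Working it through.** No sample size, power or error rate is involved, so the check sets the texts side by side.

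**Step 1. Apply each holding text to the same event.**

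| Event | Hold-both sentence with Table 4 | Immune-related paragraph | Overlapping-toxicity text |
|---|---|---|---|
| Grade 2 diarrhoea, mid-cycle, attributed to lenvatinib | Hold both | Double hold not triggered | Interrupt lenvatinib only |
| Grade 2 AST/ALT elevation, mid-cycle, cause undetermined | Hold both | Triggered only if judged immune-related | Interrupt lenvatinib only |
| Grade 2 to 4 hypothyroidism, found at cycle start | Continue pembrolizumab | No hold recommended | Lenvatinib can be interrupted; pembrolizumab should be held |

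Each row gives different instructions, and no text ranks them.

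**Step 2. Does the link to Table 4 remove the conflict?** Not fully. If Table 4 reached only events judged immune-related, the clause about attributing an event to lenvatinib alone would have nothing to act on. The restart text also provides for toxicity attributed to lenvatinib alone, so the hold was evidently meant to reach such events.

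**Step 3. Hepatic events.** Above 5 times the upper limit of normal, with a normal baseline, Table 4 (Grade 3 or higher) permanently discontinues pembrolizumab. The combination stopping rule for elevation lasting more than 2 weeks then assumes that lenvatinib may still be given at a reduced dose. The hold-both sentence would have stopped lenvatinib too. The restart text provides for resuming the combination or pembrolizumab alone, and never lenvatinib alone.

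**Step 4. Table references.** The first hepatic stopping rule cites Table 6 with an unfilled placeholder, but Table 6 (Section 6.1.4.5) covers imaging and treatment after progression. The second cites two tables by placeholder only, one of them for lenvatinib. Neither lenvatinib's hepatic rule nor its place in the sequence can be looked up from these references.

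**Step 5. Scope of the steroid sentence.** Its trigger is suspected relation to treatment plus severity at onset or rapid worsening. It states no immune-related condition; Table 4 does. A severe overlapping event thought to be caused by lenvatinib therefore falls under item 2 but outside Table 4's steroid instructions. The subsection's heading and order suggest that single-drug events are outside item 2: the text first sets apart lenvatinib's own risks ("hypertension, arterial thrombotic events, proteinuria, and hemorrhagic events are known risks for lenvatinib treatment") and then turns to events that either drug may cause. Item 2 does not state that limit.

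**Step 6. The endpoint.** The documents give no expected rates of adverse events or interruptions, so no effect size can be derived. Only the direction can be stated: the hold-both reading records a pembrolizumab hold that the lenvatinib-only reading may not. For scale, with 30 participants one participant classified differently moves a proportion by 1/30 = 3.3 percentage points. That is the resolution of the endpoint, not an estimate of the effect.

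**The case against.** The strongest reply is that much of this is a diagnostic sequence. Mid-cycle, no pembrolizumab dose is due, so interrupting lenvatinib alone costs nothing on the pembrolizumab side. If the patient does not recover, the text directs staff to consider an immune-related event, which leads to Table 4. This stands in part. For many mid-cycle events that settle quickly, the conflict may have no practical effect. It matters if the event persists to the next infusion, in whether a pembrolizumab hold is recorded, and for hypothyroidism found at cycle start.

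On the endpoint, lenvatinib is interrupted under either reading of a mid-cycle diarrhoea case, so a count of any interruption may not change. Section 6.1.2.1 already records action taken with trial treatment, and Appendix 5 permits single-agent causality. This also stands in part. However, Section 6.1.2.1 does not require the action to be recorded per drug, and Appendix 5 generally assigns causality to the whole regimen. The hypothyroidism case can change even the overall count.

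Three stronger readings are tempting, and the documents do not support them.

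- A reader might infer that steroids are required for every severe treatment-related event. Item 2 is worded as a recommendation, needs severity at onset or rapid worsening, makes two exceptions (hypothyroidism among them), and sits in text about overlapping toxicities.
- A reader might take Section 5.3.3 to confine Table 4 to pembrolizumab-related events. It does not use exclusive wording, and it can be read as covering steroids and supportive care while the hold-both sentence covers holds. It adds to the need for reconciliation but is not a flat contradiction.
- A reader might calculate a missed pembrolizumab dose and a long steroid taper for a lenvatinib-attributed event. That carries over Table 4's steroid and taper instructions, which concern immune-related events. The hold-both sentence extends only the hold.

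**Conclusion.** The holding instructions conflict for toxicities covered by both Table 4 and the overlapping-toxicity text, and the protocol gives no order of precedence. Diarrhoea, liver enzyme elevation and hypothyroidism are the cases that the documents themselves supply. The hepatic stopping rules add an assumption about lenvatinib that does not fit the hold-both sentence, along with references that cannot be followed. The scope of the steroid sentence is suggested by its setting but not stated.

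The size of the effect on the secondary endpoint is unknown and cannot be derived from the documents. The conclusion rests on reading the current text as written, and on treating the clause about attribution to one drug as meant to have effect. It takes no position on which clinical rule is right. The inconsistency bears on safety and is cheap to remove, so it should be corrected.

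**What to change.** 1. Reconcile the Attribution and Holding paragraphs, Table 4 and its note on other events, the overlapping-toxicity text with its hepatic stopping rules, and Section 5.3.3 into one precedence statement. For suspected immune-related, lenvatinib-specific and undetermined overlapping events, it should say which drug or drugs a hold applies to and whether Table 4's steroid column applies. The content is for the sponsor's clinical lead.
2. State which events item 2 covers.
3. Replace the placeholder and incorrect table references with the tables intended.
4. Record action taken separately for lenvatinib and pembrolizumab on the case report form, and report the Section 3.2 interruption, reduction and discontinuation endpoint per drug and overall.

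The cost is one amendment to Section 5.2.2 with a matching line in Section 5.3.3, one extra case report form field per adverse event, and slightly more tabulation.
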